2.2 Background

2.2.1 Description of HMPL-306

HMPL-306 is a highly selective, potent inhibitor that targets mutant IDH1/IDH2, which is characterized by a high oral bioavailability, a low clearance rate, an extensive tissue distribution, a relatively low risk of drug-drug interactions, and satisfactory preclinical safety features. HMPL-306 is available in tablet formulation of 2 strengths: CCI mg and CCI mg.

2.2.2 Supportive Nonclinical Data

2.2.2.1 Pharmacology

Further details on pharmacology are provided in the Investigator's Brochure (IB).

2.2.2.1.1 *In Vitro* Pharmacodynamics

In an *in vitro* enzyme activity study with IDH1 mutation, HMPL-306 showed intermediate inhibitory activity on the IDH1-R132H mutant, which exhibits selectivity compared to its inhibitory activity on wild-type IDH1 enzyme. In the *in vitro* enzyme activity study of IDH2 mutations, HMPL-306 had strong inhibitory activity on IDH2-R140Q and IDH2-R172K mutant enzymes, similar to the activity of positive control compound AG-221 and had high selectivity (~18 times) compared to its inhibitory activity on wild-type IDH2 enzyme. HMPL-306 also significantly inhibits the production of 2-HG in multiple mutant IDH cell lines.

HMPL-306 has CCI effect on CCI or on 322 kinases in the SelectScreen™ platform, showing high kinase selectivity. On the CEREP platform, CCI, HMPL-306 did not show CCI.

2.2.2.1.2 *In Vivo* Pharmacodynamics

Target inhibitory effect of HMPL-306 on 2-HG in U87MG-IDH2R140Q-M31 tumor model

Following [REDACTED] dose administration of HMPL-306, the inhibitory effect against 2-HG increased with the dose and drug concentration, showing good PK/PD correlation. The inhibitory effect on 2-HG after administration of HMPL-306 at [REDACTED] mg/kg [REDACTED] showed that 24 hours after the last dose, HMPL-306's inhibitory rate on 2-HG was maintained at more than 96%, and the inhibitory rate was significantly higher than that after a single dose at the same dosage.

Target Inhibitory effect of HMPL-306 on 2-HG in HT1080-IDH1R132C tumor model

HMPL-306 was administered at [REDACTED] mg/kg, and the target inhibition of HMPL-306 on IDH1 mutation was evaluated by measuring changes of 2-HG levels after 2 to 40 hours. The results showed that, at 16 and 24 hours after dosing in all dose groups, the inhibitory rate of HMPL-306 against 2-HG in tumor tissues reached more than 90%. After [REDACTED] mg/kg [REDACTED], 2-HG inhibition rate in tumor tissues reached 97%. Compared with the results of [REDACTED] mg/kg, its inhibitory effect on the target was stronger with the increase in drug exposure after [REDACTED].

2.2.2.1.3 Safety Pharmacology

The effect of HMPL-306 on hERG potassium channels expressed in transfected human embryonic kidney (HEK293) cells: The IC₅₀ of HMPL-306 was [REDACTED] μM on hERG potassium channels.

A study on the effect on cardiovascular system: [REDACTED] were observed following a single dose of [REDACTED], and [REDACTED] mg/kg of HMPL-306 in Beagle dogs. The no observed adverse effect level (NOAEL) of was [REDACTED] mg/kg.

A study of the effect on the central nervous system (CNS): [REDACTED] following a single dose of [REDACTED] and [REDACTED] mg/kg of HMPL-306 in Sprague-Dawley rats. The NOAEL for the CNS was [REDACTED] mg/kg.

A study on the effect on the respiratory system: [REDACTED] following a single dose of [REDACTED], and [REDACTED] mg/kg of HMPL-306 Sprague-Dawley rats. The NOAEL was [REDACTED] mg/kg.

2.2.2.2 Toxicology

The completed toxicological studies of HMPL-306 included: studies on single-dose toxicity in rats and dogs, 4-week repeated dose toxicity studies with an 8-week recovery period in rats and dogs, and genetic toxicity tests combination study (bacterial response mutation test, chromosome aberration test, *in vivo* micronucleus test).

The results of toxicology tests showed that after HMPL-306 was given to rats and dogs in a single dose, [REDACTED], and the maximum tolerated dose was [REDACTED] mg/kg and [REDACTED] mg/kg, respectively.

In the repeated-dose toxicity study of rats and dogs, [REDACTED] in the two species. In rats, [REDACTED] were observed. In rats, the NOAEL of HMPL-306 API was [REDACTED] mg/kg and the highest non-severely toxic dose (HNSTD) was [REDACTED] mg/kg. [REDACTED] were observed in dogs. The NOAEL and HNSTD of HMPL-306

API in dogs were determined to be [REDACTED] mg/kg in female dogs and [REDACTED] mg/kg in male dogs respectively. The common target organ of rats and dogs was [REDACTED]. The changes in the [REDACTED] were also observed in the high-dose group of rats at the end of the dosing period. After the 8-week recovery period, except that the [REDACTED] in the high-dose female rat group, the other changes mentioned above had recovered.

The results of the [REDACTED]

Further details on toxicology are provided in the IB.

2.2.2.3 Pharmacokinetics

HMPL-306 has [REDACTED] in rats and dogs, [REDACTED], and [REDACTED]; it is widely distributed in rats, with the [REDACTED]. The exposure of HMPL-306 in the [REDACTED]. The main *in vivo* metabolites in rats were the [REDACTED]. HMPL-306 was mainly [REDACTED]. Drug interaction of HMPL-306 may come largely from: 1) [REDACTED] by HMPL-306; 2) [REDACTED] by HMPL-306; 3) The impact of other drugs on the major metabolic enzymes [REDACTED] of HMPL-306.

Further details on pharmacokinetics are provided in the IB.

2.3 Benefit/Risk Assessment

2.3.1 Risk Assessment

HMPL-306 is in the early stage of development, and the clinical safety profile has not yet been established, but some potential risks have been observed from nonclinical studies and clinical data from drugs in the same class. Measures for managing these potential risks are as shown in [Table 3](#).

Table 3 Summary of Potential Risks of HMPL-306

Potential Risk of Clinical Significance	Summary of Data/Rationale for Risk	Mitigation Strategy
Gastrointestinal disorders	[REDACTED] was observed in rats with doses up to [REDACTED] mg/kg of HMPL-306. Gastrointestinal diseases such as nausea, vomiting, diarrhea, mucositis, constipation, abdominal pain, etc. occurred in clinical studies of both enasidenib and ivosidenib.	General guidance to be provided in the protocol for dose interruption/reduction/discontinuation in response to AEs.
Embryotoxicity	At the present stage, the study of effect of HMPL-306 on embryo development has not been implemented. Enasidenib and ivosidenib were associated with maternal toxicity and adverse embryo-fetal effects in pregnant rats.	Women who are pregnant (pregnancy test is positive before drug administration) or breastfeeding will be excluded from the study. Male with partners of childbearing potential or female subjects of childbearing potential will be required to use effective contraception

Table 3 Summary of Potential Risks of HMPL-306

Potential Risk of Clinical Significance	Summary of Data/Rationale for Risk	Mitigation Strategy
		methods. Female subjects of childbearing potential will be tested for pregnancy at every cycle.
Non-infectious leukocytosis	Neutrophil count was seen increased by CCI% in animals administered HMPL-306 (CC mg/kg/day), and no abnormalities were observed at the end of the recovery period. Non-infectious leukocytosis occurred in clinical trials of both enasidenib and ivosidenib.	Peripheral white blood cell count will be monitored at baseline and during the study at regular intervals, particularly at least once weekly in the first 2 cycles (28 days/cycle) of the initial drug administration. Afterward, it will be monitored once a cycle.
Abnormal hepatic function	In the HMPL-306 high-dose (CC mg/kg/day) group in rats, the CCI showed a CCI% increase and CCI showed CCI% increase. In clinical trials of both enasidenib and ivosidenib, AEs of abnormal hepatic function occurred, including elevated liver enzymes and elevated bilirubin.	Liver function will be routinely monitored.
Eye disorders	A total of 3 rats in the medium-dose (CC mg/kg/day) and high-dose (CC mg/kg/day) groups were found to have CCI. Considering that it is a vital functional organ, ophthalmological examination will be added to the clinical trials.	Ophthalmologic examinations will be performed during the Screening. If the subject has undergone the relevant examinations 60 days before treatment, they will not be required to repeat the test for Screening. After the start of treatment, ocular appearance, and slit lamp examinations will be performed every 3 cycles (ie, Day 1 of Cycles 4, 7, and 10) and during the end of treatment visit. Other ophthalmic examinations will be performed when clinically indicated.
Male reproductive system lesions	In rats given a medium-dose of HMPL-306 (CC mg/kg/day), CCI. In the high-dose (CC mg/kg/day) group, CCI.	Male subjects of childbearing potential will be included only if they agree to use effective contraception methods during the study and within 180 days after the last administration of the study drug.
Pancreatic lesions	CCI was observed in male rats administered with a high-dose of HMPL-306 (CC mg/kg/day) and was not observed during the recovery period.	Serum lipase and amylase will be monitored.
QTcF Interval Prolongation	The inhibitory rate of the negative reference standard and positive reference standard to the hERG potassium current of HMPL-306	QTcF will be monitored throughout the study, and dose modification guidelines are presented for associated AEs based on CTCAE grading criteria.

Table 3 Summary of Potential Risks of HMPL-306

Potential Risk of Clinical Significance	Summary of Data/Rationale for Risk	Mitigation Strategy
	
was within acceptable range (IC_{50} was as high as CCI μM).
 
CCI, QTcF interval prolongation has been seen as a class effect with other approved IDH inhibitors and may be seen with HMPL-306.
	

AE = adverse event; CTCAE = Common Terminology Criteria of Adverse Events; hERG = human Ether-à-go-go-Related Gene; IC_{50} = half-maximal inhibitory concentration; QTcF = interval from start of the Q wave to the end of the T wave interval corrected for heart rate using Fridericia's formula.

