Visit Frequency	
Cycle 1: every week (±1 day, except D1)
 
Cycle 2: every 2 weeks (±1 day)
 
Cycle 3 and onward: Day 1 (±3 days)
 
End of Treatment: within 7 days (±3 days) after the last dose
 
For Cohort C-1:
 
Pre-surgery: every week (±1 day, except D1)
 
Cycles 1 and 2: every 2 weeks (±3 days)
 
Cycle 3 and onward: Day 1 (±3 days)
 
End of Treatment: within 7 days (±3 days) after the last dose

Number of Participants	
Part 1: at least 1 subject will be enrolled to dose levels 1, 2, and 3. At least 3 subjects will be enrolled to dose levels 4, 5, 6, 7, and 8.
 
Part 2: approximately 20 evaluable subjects (15 subjects in Cohort C-1) per cohort will be enrolled; for a total of approximately 95 subjects

Intervention Groups and Duration	
Part 1: CCI, and CCI mg of HMPL-306 PO QD administered to dosing groups for 28 days cycles
 
Part 2: MTD/RP2D as determined in Part 1, administered PO QD to approximately 95 subjects for 28-day cycles

Data Monitoring/Other Committee	Yes

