1.3 Schedule of Events

The schedule of events (SOE) is presented in [Table 1](#) and [Table 2](#).

Table 1 Schedule of Events (excluding Cohort C-1)

Cycle/Period	Pre- screening	Screening	C1				C2		C3+	EOT	Safety Follow- up	Efficacy Follow- up	Survival Follow- up
Visit			D1	D8	D15	D22	D1	D15	D1	Within 7 Days After the Last Dose	30 Days After the EOT Visit	Every 12 Weeks From EOT Visit	Every 12 Weeks From EOT Visit
Visit Window (days)	--	-28 to -1	--	±1	±1	±1	±1	±1	±3	±3	±7	±14	±14
Activities													
Pre-screening informed consent ¹	X												
Main informed consent ²		X											
IDH mutational status ³	X	X								X			
Medical history and demographics ⁴	X	X											
Prior and concomitant medications and concomitant procedures ⁵		X	X	X	X	X	X	X	X	X	X	X	
Height		X											
Physical examination, vital signs, and weight ⁶		X	X	X	X	X	X	X	X	X			
ECOG performance status ⁶		X	X		X		X	X	X	X			
Ophthalmologic examination ⁷		X						X (±1 week)	Every 12 weeks (±1 week) from C4D1				
Laboratory evaluations ⁶													
Hematology ⁸		X ⁹		X	X	X	X	X	X	X	X		
Blood chemistry ¹⁰		X ⁹		X	X	X	X	X	X	X	X		
Blood amylase and lipase		X ⁹		X	X	X	X	X	X	X			
Fasting lipid panel ¹¹		X ⁹			X		X		X	X			
Coagulation indicators ¹²		X ⁹			X		X		X				
Pregnancy test ¹³		X	X				X		X	X	X		
Urinalysis ¹⁴		X ⁹					X		X	X			

Table 1 Schedule of Events (excluding Cohort C-1)

Cycle/Period	Pre-screening	Screening	C1				C2		C3+	EOT	Safety Follow-up	Efficacy Follow-up	Survival Follow-up
Visit			D1	D8	D15	D22	D1	D15	D1	Within 7 Days After the Last Dose	30 Days After the EOT Visit	Every 12 Weeks From EOT Visit	Every 12 Weeks From EOT Visit
Visit Window (days)	--	-28 to -1	--	±1	±1	±1	±1	±1	±3	±3	±7	±14	±14
Activities													
Virological screening ¹⁵		X											
HbA1C		X ⁹			X		X		X	X			
PK and PD assessments	Refer to Appendix 1												
12-lead ECG ^{6,16}	Refer to Appendix 1												
ECHO/MUGA scan		X					X		C3D1 then Day 1 of every odd cycle (ie, C5D1, C7D1, etc.) (±1 week)				
Tumor evaluation/imaging ¹⁷		X	Every 8 weeks from C1D1 during the first 24 (±1) weeks and every 12 (±2) weeks thereafter								X		
Tumor tissue for exploratory biomarker evaluation. Applies to Cohorts A, B, and D only ¹⁸		X					X±7 days		At disease progression only in dose expansion				
Blood for gene mutation analysis ¹⁹		X	Only in dose expansion; refer to Appendix 1										

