- ^{7.} Ophthalmologic assessments, including eye appearance, slit lamp examination, best corrected visual acuity, visual field, eye movement, pupil reflex, optical coherence tomography (OCT), and intraocular pressure will be performed during the Screening Period. If the subject has undergone the relevant examinations 60 days before the start of study treatment (C1D1), they need not be repeated. After the start of study drug administration, OCT will be performed at 6 weeks (± 1 week), then OCT, eye appearance, and slit lamp examinations will be performed every 12 weeks (± 1 week) from C4D1 and at the EOT visit. Other ophthalmic examinations are to be performed when clinically indicated. If the subject develops an ophthalmic AE related to HMPL-306, the frequency of the examination should be increased to once every cycle until the adverse event is relieved or stable.
- ^{8.} Hematology includes red blood cell count, hemoglobin, hematocrit, white blood cell count with differential and classifications (absolute neutrophil count, neutrophils % absolute lymphocyte count, lymphocytes %, absolute eosinophil count, eosinophils %, absolute monocyte count, monocytes %, absolute basophil count and basophils %), and platelet count. If abnormal or primitive immature cells are seen, they are also required to be recorded. Any additional routine blood tests during the study shall be arranged by the investigator as needed.
- ^{9.} These tests should be completed within 7 days before the start of treatment; if completed more than 7 days before the first dose, they must be repeated on C1D1 prior to dosing.
- ^{10.} Blood chemistry includes blood urea nitrogen, creatinine, sodium, potassium, magnesium, chloride, calcium, phosphorus, blood glucose, creatine phosphokinase, total bilirubin, direct bilirubin, indirect bilirubin, ALT, AST, ALP, LDH, total protein, and albumin.
- ^{11.} Fasting lipid panel includes total cholesterol, high-density lipoprotein, low-density lipoprotein, and triglycerides.
- ^{12.} Coagulation indicators include PT, aPTT, and INR.

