2.3.3 Overall Benefit/Risk Conclusion

At present, there are no IDH1 and/or IDH2 inhibitors approved for treatment of the types of cancers being studied in this clinical trial.

HMPL-306 is a dual inhibitor of IDH1 and IDH2, which, in preclinical studies, has demonstrated similar efficacy to single-target IDH inhibitors (ivosidenib), and may have similar benefit to other IDH1 and/or IDH2 inhibitors in the same class.

Preclinical studies, including toxicology studies, indicate that HMPL-306 is well tolerated.

Taking into account the measures taken to minimize risk to participants in this study, the potential risks identified in association with HMPL-306 are justified by the anticipated benefits that may be afforded to participants with solid tumors with IDH mutations as defined in Section 5.2.

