6.1.10.1 Hematology

Hematology, including red blood cell count, hemoglobin, hematocrit, white blood cell count with differential and classifications (neutrophils [ANC and neutrophils %], lymphocytes [absolute lymphocyte count and lymphocytes %], eosinophils [absolute eosinophil count and eosinophils %], monocytes [absolute monocyte count and monocytes %], and basophils [absolute basophil count and basophils %]), and platelet count, will be performed during the study according to the schedule in [Table 1](#) and [Table 2](#). If abnormal or primitive immature cells are seen, they will also be recorded. Any additional routine blood tests during the study shall be arranged by the investigator as needed.

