7.5 Special Adverse Events Handling Principles

7.5.1 Handling Principles for Leukocytosis

Subjects who develop leukocytosis should be graded per NCI CTCAE Version 5.0 and treated by the following measures in a timely manner:

- Hydroxyurea oral therapy is immediately given, and it can be used at up to 2 to 3 g twice a day (see [Table 10](#))
- Leukapheresis is performed if clinically necessary

When the above treatment measures are unable to effectively control the clinical symptoms, HMPL-306 treatment should be suspended. After the clinical symptoms have been fully relieved, the HMPL-306 administration can be resumed. The dose of the drug resumed should be decided after discussion with the Sponsor-appointed medical monitor.

Table 10 Hydroxyurea Initial Dose Reference

Hydroxyurea Dose	Peripheral White Blood Cell Count	Absolute Value of Increase from Baseline of Peripheral White Blood Cell Count
1000 mg QD	$25 \times 10^9/L$ to $50 \times 10^9/L$	$15 \times 10^9/L$ to $<30 \times 10^9/L$
2000 mg BID	$>50 \times 10^9/L$ to $75 \times 10^9/L$	$30 \times 10^9/L$ to $<50 \times 10^9/L$
3000 mg BID	$>75 \times 10^9/L$	$\geq 50 \times 10^9/L$

BID = twice daily; QD = once a day.

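### The risk table sets white-cell counts at least weekly through Cycle 2 for leukocytosis, but the schedule takes them only every 2 weeks in Cycle 2

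*Protocol*

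**What the plan says.** Section 2.3.1, Table 3, lists non-infectious leukocytosis as a potential risk on two grounds: a neutrophil rise in animals given HMPL-306, and cases in clinical trials of two other IDH inhibitors. The mitigation column contains one measure, monitoring of the white-cell count. Counts are to be taken at baseline and at intervals, "particularly at least once weekly in the first 2 cycles (28 days/cycle) of the initial drug administration", then once a cycle.

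The operational parts of the protocol say something else for Cycle 2:

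- The synopsis, under visit frequency, has "Cycle 2: every 2 weeks (±1 day".
- Section 1.3, Table 1, marks hematology at screening, C1D8, C1D15, C1D22, C2D1, C2D15 and Day 1 of each later cycle. It has no C2D8 or C2D22 visit.
- Section 6.1.10.1 sets no separate rule for white cells. The full panel, white-cell count through differential "and platelet count, will be performed during the study according to the schedule in" Tables 1 and 2.
- Footnote 8 to Table 1 adds: "Any additional routine blood tests during the study shall be arranged by the investigator as needed".

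Section 7.5.1 makes treatment depend on the count. On leukocytosis, "Hydroxyurea oral therapy is immediately given, and it can be used at up to 2 to 3 g twice a day", with the starting dose taken from Table 10 by white-cell band or by the absolute rise from baseline. Section 2.3.3 then weighs the risks against what subjects may gain and concludes: "Taking into account the measures taken to minimize risk to participants in this study, the potential risks identified in association with HMPL-306 are justified".

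**The concern.** Table 3 states a minimum frequency, and a site that follows Table 1 exactly falls below it in Cycle 2. The shortfall concerns the only mitigation Table 3 gives for this risk, and the benefit-risk conclusion rests on such measures being in place.

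The consequence is clinical. A rise in white cells without symptoms triggers nothing until somebody counts. If the next scheduled count is two weeks away instead of one, hydroxyurea, which Section 7.5.1 wants given at once and at a dose set by the count, can start correspondingly later.

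**Working it through.** The plan states no figure of its own here, so the check is a count of scheduled days against a 7-day grid.

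**Inputs.** Cycles are 28 days. Hematology days come from Table 1. Visit windows are ±1 day in Cycles 1 and 2 and ±3 days from Cycle 3 (Table 1 header and footnote 6). The weekly minimum over two cycles comes from Table 3.

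**Study days**, with C1D1 as day 1:

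- Weekly grid after the first dose: 8, 15, 22, 29, 36, 43, 50, which is 7 counts.
- Table 1: 8, 15, 22, 29, 43, which is 5 counts.
- Missing: day 36 (C2D8) and day 50 (C2D22).

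Within Cycle 2 alone, weekly means D1, D8, D15 and D22. Table 1 has D1 and D15, so 2 of 4. The pre-dose baseline count is left out of these totals because Table 3 names baseline separately and footnote 9 lets it fall up to 7 days before dosing.

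**Gaps.** The nominal gap is the difference in study days. The widest gap within windows adds the early margin of the first visit and the late margin of the second.

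| Interval | Nominal (days) | Widest within windows (days) |
|---|---|---|
| C1D8 to C1D15, C1D15 to C1D22, C1D22 to C2D1 | 7 | 7 + 1 + 1 = 9 |
| C2D1 to C2D15 | 43 − 29 = 14 | 14 + 1 + 1 = 16 |
| C2D15 to C3D1 | 57 − 43 = 14 | 14 + 1 + 3 = 18 |

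The nominal ratio is 14/7 = 2. In the first half of Cycle 2 the widest-gap ratio is 16/9, about 1.8. In the second half, an added C2D22 count would still be followed by C3D1 with its ±3-day window, so the weekly comparator there is 7 + 1 + 3 = 11 days and the ratio is 18/11, about 1.6.

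**Where the mismatch lies.** Cycle 1 is weekly and agrees with Table 3. From Cycle 3, once a cycle agrees as well. Only Cycle 2 fails.

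**Whether another provision fills the gap.** The extra-tests sentence in footnote 8 is discretionary and sets no minimum. Appendix 1 has a C2D2 time point, but for a PK sample only. Section 7.5.1 gives treatment steps and no monitoring frequency. None of these supplies a C2D8 or C2D22 count.

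**The case against.** The strongest reply is that Table 3, not the schedule, may be the text in error. The synopsis, Table 1 and Section 6.1.10.1 agree with one another, and Table 3 stands alone. Table 3 also lags the schedule elsewhere: its eye-disorder row omits the 6-week optical coherence tomography that Table 1 footnote 7 requires and that Amendment 1 introduced. This stands as far as it goes. It means that correcting Table 3 is a legitimate remedy, but the two texts still cannot both hold, and lowering a stated safeguard needs a reason.

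The second reply is that the harm is limited. Section 4.1.1 reports neither dose-limiting toxicity nor a safety concern at the first four dose levels. Unscheduled examinations are allowed when clinically indicated. Interruption of the drug turns on symptoms: "When the above treatment measures are unable to effectively control the clinical symptoms, HMPL-306 treatment should be suspended". This also stands. A subject with symptoms need not wait for C2D15, so what remains is the asymptomatic rise between visits, for which only a scheduled or discretionary count would start treatment.

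Two further inferences are tempting, and the documents do not support them:

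- A reader might try to put a probability on missing a rise. That needs the duration of a rise, a distribution of onset and an assumption of no unscheduled counts, and the documents supply none of these.
- A reader might infer that the SAP's shift table to the worst post-baseline laboratory grade (SAP 5.2.11.4) is biased downward. That table uses scheduled and unscheduled values over the whole treatment period. The grading criteria sit in a SAP appendix that is not in the supplied text, so whether a high white-cell count is graded at all cannot be checked.

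**Conclusion.** The mismatch is real in the supplied protocol (Amendment 2) and confined in Table 1 to Cycle 2. The schedule gives 2 of 4 weekly counts in that cycle and 5 of 7 post-first-dose counts over two cycles, with 14-day nominal gaps (16 to 18 within windows) where Table 3 implies 7 (9 within windows). An asymptomatic rise can go uncounted for about twice the intended time, and count-based hydroxyurea can be delayed accordingly. This should be corrected, because the schedule omits part of a named safeguard and the correction is cheap.

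The conclusion assumes that sites keep to Table 1 and take no extra counts. It does not show that any event was missed or treated late, since no incidence of leukocytosis is given. Nor does it touch dose escalation: the DLT window is C1D1 to C1D28, where counting is weekly. The SAP states that the expansion part enrolled nobody, so any practical effect falls on Part 1 subjects. The SAP is written against Amendment 3, which was not supplied, so whether the mismatch was later corrected is unknown.

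**What to change.** Add hematology on C2D8 and C2D22 to Table 1 as blood-only draws, without a full visit; a local laboratory is acceptable. The cost is two extra blood counts per subject in Cycle 2 and two entries in Table 1. At the planned Part 1 size of 27 to 36 subjects this is at most 2 × 27 = 54 to 2 × 36 = 72 draws, a ceiling reached only if every subject completes Cycle 2.

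If the sponsor judges from the data so far that 2-weekly counts are enough, it should instead change Table 3 to weekly in Cycle 1, every 2 weeks in Cycle 2 and once a cycle afterward, and state the justification there. That costs a wording change and a short rationale. First check whether Amendment 3 has already made either change.
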